5.4. Secondary Endpoint(s) Analysis

All secondary endpoints analysis will be based on the full analysis set.

5.4.1. Secondary Endpoints of Special Interest

5.4.1.1. Snaith-Hamilton Pleasure Scale (SHAPS)

5.4.1.1.1. Definition

The SHAPS is a reliable, valid, and unidimensional instrument to assess hedonic capacity in adults with Major Depressive Disorder in the last few days. It is a 14-item, self-report tool with a completion time below 5 minutes. Each of the items has a set of 4 response categories: 1=Definitely Agree/Strongly Agree, 2=Agree, 3=Disagree, and 4=Strongly Disagree. The SHAPS total score is the sum of the 14 item scores, ranging from 14 to 56. A higher SHAPS total score indicates higher levels of current anhedonia (Nakonezny 2010).

Negative changes in the SHAPS total score indicate improvement.

5.4.1.1.2. Analysis Methods

Descriptive statistics of the actual values at Baseline, Week 6, and the change from baseline to Week 6 will be presented for SHAPS total score by intervention group.

An analysis of covariance (ANCOVA) model will be used to test the difference of change from baseline at Week 6 in SHAPS total score between JNJ-55308942 mg once daily and placebo. The model will include intervention (placebo or JNJ-55308942), BD type (I or II), country, P2RX7 GoF SNP mutation genotype (homozygous or heterozygous), and concomitant medication status (no mood stabilizer or antipsychotic, a mood stabilizer alone, an antipsychotic alone, or a combination of a mood stabilizer and an antipsychotic) as factors, and baseline SHAPS total score as a covariate. Comparison between JNJ-55308942 mg once daily and placebo will be performed using appropriate contrast. Difference of least square means and 2-sided 80% CI will

be presented. Least square means of change from baseline (+/- SE) to Week 6 will be presented graphically.

Frequency distributions of the SHAPS individual items will be provided at each assessment time point.

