9.2. Sample Size Determination

The estimated sample size of 164 participants (82 participants per group) was determined based on the assumption of an effect size of at least 0.45 for the MADRS total score (difference in mean change from baseline at Week 6 between the JNJ-55308942 and placebo groups of 3.9 units with a standard deviation of 8.6). This is considered to be a clinically relevant difference in a population with BD types I or II. The standard deviation of 8.6 in the change in MADRS total score from baseline is a reasonable assumption based on data in a published phase 3 study of quetiapine in BD type I and type II depression ([Calabrese 2005](#)). Power is set at 90%, with a 1-sided alpha of 0.10 and a 6-week drop-out rate of 20%. The estimated number of completers to be included in the primary analysis is 132.

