Participants who are enrolled in the study will continue on their current medication regimen, if applicable, throughout the study. No dose changes are permitted from screening through the end of the study (until after the follow-up visit). No concurrent use of antidepressants will be allowed until after the follow-up visit.

For each participant, the study will consist of 3 phases: a screening phase of up to 4 weeks, a double-blind treatment phase of 6 weeks, and a post-treatment follow-up phase of up to 2 weeks (Figure 1). After giving written informed consent for screening, participants will be screened between 28 days and 1 day before the double-blind treatment phase to ascertain their eligibility for the study according to the inclusion and exclusion criteria. Eligible participants will enter the double-blind treatment phase where they will be randomly assigned with a 1:1 ratio to once daily administration with mg JNJ-55308942 or placebo for 6 weeks, Day 1 up to and including the last treatment visit, Day 43 +/- 1 day. Between approximately 1 to 2 weeks after administration of the last dose, participants will return to the study site for a follow-up visit. The total study duration for each participant will be up to 12 weeks. There will be 7 scheduled visits to the study site during the study, including screening and follow-up visit.

Treatment Period Follow-up Visit Screening (Efficacy/Safety) **Study complete** Up to 4 weeks Double-blind, 6 weeks BD type I and II in a current MDE All participants 1-2 weeks **Include GoF P2X7 mutation** Placebo Exclude complete LoF P2X7 mutations JNJ-55308942 Up to 4 weeks 6 weeks At 6 weeks: **Primary endpoint MADRS**

Figure 1: Schematic Overview of the Study

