3. SAMPLE SIZE DETERMINATION

The estimated sample size of 164 participants (82 participants per group) was determined based on the assumption of an effect size of at least 0.45 for the MADRS total score (difference in mean change from baseline at Week 6 between the JNJ-55308942 and placebo groups of 3.9 units with a standard deviation of 8.6). This is considered to be a clinically relevant difference in a population with BD types I and II. The standard deviation of 8.6 in the change in MADRS total score from baseline is a reasonable assumption based on data in a published phase 3 study of quetiapine in BD type I and type II depression (Calabrese 2005). Power is set at 90%, with a 1-sided alpha of 0.10 and a 6-week drop-out rate of 20%. The estimated number of completers to be included in the primary analysis is 132.

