5.1.3. Imputation of Efficacy

Imputation for missing data will include the following methods (Table 3).

Table 3: Imputation of Missing Efficacy Data

Imputation	Text
Multiple Imputation (MI)	1) Copy Reference
method	2) Delta Adjustment.
Non-Responder	Participants with missing values will be imputed as non-responders.
Non-Remitter	Participants with missing values will be imputed as non-remitters.

Imputation of total scores will apply only to the MADRS. Imputation of the MADRS total score will be performed only when 1 item score is missing. If 2 or more items are missing, the total score will be left missing. The total score will be imputed by calculating the sum of the scores of the non-missing items and multiplying it by the ratio of the maximum possible number of items (i.e., 10) to the number of non-missing items (i.e., 9).

For all other efficacy scales where multiple items are summed to create a total score, if any item of the scale is missing on one visit, the total score for that scale at that visit will be left missing.

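### The SHAPS ANCOVA drops participants without a post-baseline SHAPS and ignores their recorded MADRS course, although the protocol withdraws participants whose depression worsens

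*SAP*

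**What the plan says.** - **Schedule.** Protocol 1.3 and 4.1 place SHAPS at baseline and once at the end of treatment (Day 43). None is scheduled at the follow-up or early withdrawal visit.
- **Model.** SAP 5.4.1.1.2: "An analysis of covariance (ANCOVA) model will be used to test the difference of change from baseline at Week 6 in SHAPS total score". The terms are intervention, BD type, country, genotype, concomitant medication status and baseline SHAPS. Protocol 9.4.2 agrees.
- **Missing data.** SAP 5.1.3 imputes a total score for MADRS only. For the other summed scales, "if any item of the scale is missing on one visit, the total score for that scale at that visit will be left missing". Multiple imputation appears only in the MADRS sensitivity analyses (SAP 5.3.2.1.2).
- **Analysis set.** Secondary endpoints use the full analysis set (FAS), which requires a post-baseline MADRS but not a post-baseline SHAPS (SAP 4 and 5.4).
- **Window.** SAP Table 2 labels any SHAPS from Day 2 onward as Week 6. The MADRS Week 6 window starts at Day 36.
- **Other scales.** MADRS, PROMIS, PHQ-9 and GAD-7 have MMRMs. CGI-S is descriptive. Response and remission are analysed on observed data and also with missing counted as non-response or non-remission.
- **Planned dropout.** SAP 3: "Power is set at 90%, with a 1-sided alpha of 0.10 and a 6-week drop-out rate of 20" per cent.

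**The concern.** A participant who leaves after Week 2 or Week 4 has MADRS and PHQ-9 values on record and belongs to the FAS, yet contributes nothing to the SHAPS contrast. The ANCOVA contains no post-baseline information, so it treats leavers as exchangeable with stayers who share their arm, strata and baseline SHAPS.

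The protocol makes that hard to believe. Section 7.4 withdraws participants for worsening depression that needs a new intervention, and for acute suicidal ideation. Section 4.2.2 says the same of clinically significant deterioration. Leaving therefore depends partly on the post-baseline course, which MADRS and PHQ-9 track. If the drug works, such withdrawals would fall more heavily on placebo. The placebo participants who remain would then look better than their arm as a whole, and the SHAPS difference would shrink.

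There is a second route to a missing SHAPS. Under Protocol 10.7.2 a visit affected by COVID-19 can have MADRS by phone, but site staff may not administer SHAPS by phone. Week 6 MADRS can then exist without Week 6 SHAPS.

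**Working it through.** **1. The plan's own figures.** Inputs from SAP 3 and Protocol 9.2: 1-sided alpha 0.10, power 90%, a MADRS difference of 3.9 with SD 8.6 (3.9/8.6 = 0.4535; effect size stated as at least 0.45), 20% dropout.
- n per arm = 2(1.2816 + 1.2816)²/d² = 13.14/d². This gives 64 for d = 0.4535 and 65 for d = 0.45; the t-based version gives 65 and 66.
- Completers: 130 to 132. Divided by 0.8: 163 to 165 randomized.
- Stated: "The estimated number of completers to be included in the primary analysis is 132", with 164 randomized. The figures reproduce.
- 164 × 0.8 = 131.2, so the plan allows for about 32 or 33 participants without Week 6 data.

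**2. Bias of the observed-case contrast.** Let M be the MADRS change residual and S the SHAPS change residual, each with SD 1 and correlation r. If dropout depends on M, then within an arm

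error = r × (mean of M among those observed − mean of M among all),

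and the error of the contrast is the difference between the two arms' errors. The documents give no SHAPS SD, effect or r. Assumed: true benefit 0.45 SD on both scales (borrowed from the MADRS planning value), r = 0.3, 0.5 or 0.7, and dropout probability p either constant at 0.20 or logistic in M. With 400,000 simulated participants per arm, the observed-case estimates of 0.45 are:

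| Dropout mechanism | r = 0.3 | r = 0.5 | r = 0.7 | Shortfall |
|---|---|---|---|---|
| Unrelated to M | 0.446 | 0.450 | 0.447 | none beyond simulation error |
| Same in both arms: logit p = −1.45 + M (23% placebo, 17% active missing) | 0.435 | 0.427 | 0.419 | 3%, 5%, 7% |
| Placebo only: logit p = −1.62 + M; active p constant (20% missing in each) | 0.397 | 0.364 | 0.326 | 12%, 19%, 28% |

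Example: (0.45 − 0.326)/0.45 = 28%. The estimate that uses M as auxiliary lies between 0.447 and 0.453 in all nine cells.

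**3. Further simulations, with a true effect of 0.30 SD and r = 0.6 (assumed).**
- About 20% missing: observed-case ANCOVA gave 0.29 with equal dependence in both arms and 0.22 with placebo-only dependence. The latter shortfall is (0.30 − 0.22)/0.30 = 27%. By-arm imputation with MADRS auxiliaries gave 0.30, with the SE essentially unchanged at 0.159 to 0.161. The 0.08 SD shortfall is about half a standard error (0.08/0.16).
- 164 participants, 6,000 replicates, 18 to 23% dropout driven by mid-trial MADRS: observed-case estimates of 0.285, 0.275, 0.308 and 0.323, that is −5%, −8%, +3% and +8%. The auxiliary estimate was 0.300 to 0.305. The sign is not fixed.

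**4. Precision.** With SHAPS seen on 66 of 82 per arm and MADRS on all 82, the variance ratio is (1 − r²) + r² × 66/82 = 0.982, 0.951, 0.904. Effective n per arm rises from 66 to 67.2, 69.4, 73.0. Power for 0.45 SD goes from 90.4% to 90.8%, 91.4%, 92.5%.

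**The case against.** The choice of ANCOVA is not itself inconsistent. With one post-baseline visit, the MMRM used for the other scales reduces to this ANCOVA, and it is valid under missing at random given the terms it contains. The PHQ-9, GAD-7 and PROMIS models each condition on their own earlier visits; none borrows another scale's values. The stakes are modest: a secondary endpoint in a proof-of-concept trial, with no multiplicity adjustment (Protocol 9.1) and no SHAPS power claim. Every bias input is assumed. All of this stands. It limits the size of the point but does not make the missingness assumption plausible under the withdrawal rule in Protocol 7.4.

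Three stronger readings are tempting, and the documents do not support them:

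- **SHAPS is the only scale with a stronger missing-data assumption.** CGI-S is descriptive, and the observed-data tests of response and remission carry no covariates, which is a stronger assumption still. SHAPS is the only continuous efficacy scale compared by a model that uses no earlier post-baseline values.
- **A fifth of SHAPS values will be missing.** The 20% is a planning rate for all randomized participants. The FAS already excludes those with no post-baseline MADRS, so its share may be lower. Protocol 7.2 continues scheduled assessments after treatment stops, while 7.4 withdraws those participants from the study. The two sections must be reconciled before the amount of missing SHAPS can be judged.
- **Only completed Week 6 forms enter the model.** Under Table 2, any complete form from Day 2 onward counts as Week 6. This does not rescue the analysis: an unscheduled early form would be carried forward without the SAP saying so.

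A large imputation model, with every MADRS and PHQ-9 visit fitted by arm to about 66 observed values, could be unstable. That objection is right, and the fix keeps the model short.

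**Conclusion.** The point holds as a worthwhile, low-cost improvement. SHAPS has no missing-data plan beyond an ANCOVA on observed totals, and its assumption sits badly with a rule that withdraws participants who worsen. That the model is complete-case is inferred from the SAP's silence on missing SHAPS; the SAP does not use the term.

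Under the assumptions shown, bias is about 3 to 8% of the effect when dropout depends on MADRS similarly in both arms. It is about a quarter of the effect when only placebo dropout is response-driven and the correlation is 0.6 to 0.7, and 12 to 19% at correlations of 0.3 to 0.5. It vanishes if dropout is unrelated to response. A reader might infer that the SHAPS result will be biased in a known direction. The documents give no dropout mechanism by arm, so neither sign nor size can be predicted. The case for change is protection from bias, because precision barely moves.

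The remedy is partial. MADRS is not scheduled at the early withdrawal visit, so worsening after the last MADRS visit may go unrecorded on that scale.

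**What to change.** In SAP 5.4.1.1.2:

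1. Impute missing Week 6 SHAPS totals by arm under missing at random, with 50 imputations and Rubin pooling as in 5.3.2.1.2.
2. Use baseline SHAPS, the ANCOVA factors where estimable, and a short set of auxiliaries: MADRS at baseline and Weeks 1, 2 and 4, plus Week 6 where observed. Add PHQ-9 only if the model stays stable.
3. Fit the planned ANCOVA to each completed dataset and pool. Report the observed-case ANCOVA as support.

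In SAP Table 2, start the SHAPS Week 6 window at Day 36 instead of Day 2, as for MADRS.

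The cost is SAP wording and an adaptation of the imputation steps already specified for MADRS. No new data, visits or participants are needed. The downside is one more imputation model to specify and check.

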5.4.1.2. MADRS Subgroup Analysis

5.4.1.2.1. Definition of Subgroups of Special Interest

MADRS subgroup analysis will be conducted according to the definition below.

Subgroup	Variant	Definition
P2RX7 GoF SNP mutation genotype	1	Heterozygous / Homozygous
BD type	1	I/II
Biomarker profile	1	Yes / No

5.4.1.2.2. Analysis Methods

Changes in MADRS total score at Week 6 from baseline, will be assessed in subgroups for BD type (I or II), P2RX7 GoF SNP mutation genotype (heterozygous vs. homozygous), and patients with specific biomarker profiles (yes or no). Participants will be divided into subgroups based on the definition in Section 5.4.1.2.1 to evaluate efficacy within these subgroups (i.e., evaluating change from baseline to the end of Week 6 in the MADRS total score in participants within each subgroup).

Descriptive statistics of the actual values and change from baseline at each postbaseline time point in the MADRS total score will be presented by intervention group for these subgroups. The change from baseline in the MADRS total score will be analyzed using the same MMRM described in Section 5.3.2.1.1 for each subgroup. Comparison between JNJ-55308942 mg once daily and placebo will be performed using the appropriate contrasts. Difference of least square means and 2-sided 80% CI will be presented over time. Least square means of change from baseline (+/- SE) will be presented graphically over time.

A forest plot summarizing the differences of least square means and 2-sided 80% CI between JNJ-55308942 mg once daily and placebo at Week 6 in the subgroups will be presented.

5.4.2. Other Secondary Endpoints

5.4.2.1. Clinical Global Impression – Severity (CGI-S)

5.4.2.1.1. Definition

The CGI-S provides an overall clinician-determined summary measure of the severity of the participant's illness that takes into account all available information, including knowledge of the participant's history, psychosocial circumstances, symptoms, behavior, and the impact of the symptoms on the participant's ability to function (Guy 1991). The CGI-S evaluates the severity of

psychopathology on a scale of 1 to 7. Considering total clinical experience with the depression population, a participant is assessed on severity of illness at the time of rating according to 0=not assessed; 1=normal (not at all ill); 2=borderline ill; 3=mildly ill; 4=moderately ill; 5=markedly ill; 6=severely ill; 7=among the most extremely ill patients.

A score of 0 indicates that the participant was not assessed and will be treated as missing. The score from 1 to 7 will be summarized as recorded.

Negative changes in CGI-S score indicate improvement.

5.4.2.1.2. Analysis Methods

Descriptive statistics of the actual values and the change from baseline will be presented by intervention group for observed case data.

Frequency distribution of the CGI-S scores at each scheduled time point will be provided over time by intervention group. The frequencies of CGI-S scores will be plotted over time by intervention group. In addition, frequency of shifting scale at Week 6 from baseline will be provided.

5.4.2.2. PROMIS – Ability to Participate in Social Roles and Activities

5.4.2.2.1. Definition

The PROMIS - Ability to Participate in Social Roles and Activities item bank assesses the perceived ability to perform one's usual social roles and activities. The item bank does not use a time frame (e.g., over the past seven days) when assessing the ability to participate in social roles and activities. The Short Form 4a includes 4 items that represent this concept. Each question has 5 response options ranging in value from 1 to 5 with higher scores indicating better social function. The total raw score for the short form is calculated by summing the values of the response to each question, so for the 4-item form, the lowest possible raw score is 4; the highest possible raw score is 20. The total raw score can also be converted to a T score with a mean of 50 and a standard deviation of 10 (Appendix 6.9).

5.4.2.2.2. Analysis Methods

Descriptive statistics of the actual values and the change from baseline at each post-baseline time point will be presented for PROMIS - Ability to Participate in Social Roles and Activities total T-score, total raw score, and individual items by intervention group and visit.

The change from baseline in the PROMIS - Ability to Participate in Social Roles and Activities total T-score will be analyzed using a similar MMRM as described in Section 5.3.2.1.1, with the covariate "baseline MADRS total score" changed to "baseline PROMIS - Ability to Participate in Social Roles and Activities total T-score". Comparison between JNJ-55308942 mg once daily and placebo will be performed using the appropriate contrasts. Difference in least square means and 2-sided 80% CI will be presented over time. Least square means of change from baseline (+/-SE) for PROMIS T-score will be presented graphically over time.

Frequency distributions of the individual items of the PROMIS - Ability to Participate in Social Roles and Activities will be provided at each assessment time point.

5.4.2.3. Patient Health Questionnaire – 9 (PHQ-9)

5.4.2.3.1. **Definition**

The PHQ-9 scale scores each of the 9 symptom domains of the DSM-5 major depressive disorder criteria and it has been used both as a screening tool and a measure of response to intervention for depression. Each item is rated on a 4-point scale (0=Not at all, 1=Several Days, 2=More than half the days, and 3=Nearly every day). The participant's item responses are summed to provide a total score (range of 0 to 27), with higher scores indicating greater severity of depressive symptoms. The recall period is 2 weeks.

Negative changes in the PHQ-9 total score indicate improvement.

5.4.2.3.2. Analysis Methods

Descriptive statistics of the actual values and the change from baseline to each post-baseline time point will be presented for the PHQ-9 total score and individual items by intervention group.

The analysis for changes from baseline in PHQ-9 total score at each week will be carried out using a similar MMRM as described in Section 5.3.2.1.1 for the primary efficacy endpoint, with the covariate "baseline total MADRS score" changed to "baseline PHQ-9 total score". Comparison between JNJ-55308942 mg once daily and placebo will be performed using the appropriate contrasts. Least square means of change from baseline (+/- SE) for the PHQ-9 total score will be presented graphically over time.

Frequency distributions of the PHQ-9 individual items will be provided at each assessment time point.

5.4.2.4. Generalized Anxiety Disorder – 7 (GAD-7)

5.4.2.4.1. **Definition**

The GAD-7 is a brief and validated 7-item self-report assessment of overall anxiety. Participants respond to each item using a 4-point scale with response categories of 0=not at all, 1=several days, 2=over half the days, and 3=nearly every day. The total score is the sum of item responses, ranging from 0 to 21. Higher scores indicate more anxiety.

Negative changes in the GAD-7 total score indicate improvement.

5.4.2.4.2. Analysis Methods

Descriptive statistics of the actual values and the change from baseline at weeks 2, 4, and 6 will be presented for the GAD-7 total score and individual items by intervention group for observed case data.

The analyses for changes from baseline in GAD-7 total score at weeks 2, 4, and 6 will be carried out using a similar MMRM as described in Section 5.3.2.1.1 for the primary efficacy endpoint, with the covariate "baseline total MADRS score" changed to "baseline GAD-7 total score". Comparison between JNJ-55308942 mg once daily and placebo will be performed using the appropriate contrasts. Least square means of change from baseline (+/- SE) for the GAD-7 total score will be presented graphically over time.

Frequency distributions of the GAD-7 individual items will be provided at each assessment time point.

5.4.2.5. Response Based on MADRS Total Score

5.4.2.5.1. Definition

A participant is defined as a responder at a given time point if the percent improvement from baseline in MADRS is $\geq 50\%$ at that time point (i.e., percent change $\leq -50\%$). Participants who do not meet such a criterion will be considered as non-responders. Imputation of missing response status is presented in Section 5.1.3.

